1.0 Objectives*

1.1 Overview

Allogeneic hematopoietic stem cell transplantation (HSCT) is an intensive treatment that offers a potential cure for some hematologic malignancies. The prolonged hospitalization and extended recovery is an intense experience associated with many physical symptoms and high rates of medical complications.¹ Accordingly, many allogeneic transplant recipients have substantial psychological distress² and experience diminished positive psychological well-being (PPWB; e.g., optimism, positive affect, or gratitude).³ PPWB is prospectively associated with improved quality of life (QOL), physical functioning, and survival in allogeneic recipients, independent of medical or socio-demographic variables, and above and beyond the adverse effects of depression.^{4,5,6} This suggests that there may be substantial benefit from cultivating PPWB in this population. Positive psychology interventions (PPIs) are interventions that encourage patients to perform simple, enjoyable activities (e.g., writing a gratitude letter,⁷ performing acts of kindness⁸) that consistently and durably improve PPWB in a wide variety of populations.^{9,10,11} PPIs have led to reduced depression, improved medication adherence, and more physical activity in studies of patients with a variety of medical illnesses.^{7, 10-13,9, 14}

Although PPIs have been successfully used in other medical populations,^{12, 15} they have never been tested in allogeneic transplant recipients. Informed by the Broaden and Build Theory of Positive Emotions,¹⁶ an efficacious PPI that improved PPWB in cardiac patients,¹⁷ and findings from our prior (17-154) work that explored PPWB in 25 allogeneic recipients via serial semi-structured interviews in which patients reported that positive emotional experiences resulted in increased motivation to engage in treatment and participate in health behaviors,¹⁸ we developed the Positive psychology for Allogeneic Transplantation of Hematopoietic stem cell intervention (PATH), to fill this gap. PATH is a novel 9-week phone-delivered PPI comprised of activities based in gratitude, strengths, and life purpose. We have completed a one-arm proof-of-concept study (18-225) to assess the feasibility and acceptability of the PATH intervention.¹⁹ The intervention was feasible, acceptable, and led to very small-to-medium effect size improvements in patient-reported outcomes such as optimism, positive affect, symptoms of depression and anxiety, quality of life, (QOL) and fatigue.¹⁹ This was the first proof-of-concept study to establish feasibility of a positive psychology intervention in patients with hematologic malignancy undergoing HSCT. Enhancing PPWB via PPIs in allogeneic recipients could not only improve mood, QOL, and physical functioning, but could also increase long-term survival.³

We propose to conduct a single center randomized trial of the PATH intervention versus usual care in patients with hematologic malignancies undergoing HSCT. The primary goal of this study is to further test feasibility and preliminary efficacy of a positive psychology intervention in improving clinical outcomes for patients with hematologic malignancies undergoing HSCT with a larger and more diverse patient population than we had in our one arm open pilot trial. Data from this single center trial will lay the foundation for future, larger, multi-site randomized studies to examine the efficacy of positive psychology interventions for improving outcomes in patients with hematologic malignancies undergoing HSCT.

1.2 Specific Aims/Objectives

#1 (Feasibility; Primary Aim): To determine the feasibility and acceptability of the PATH intervention in patients with hematologic malignancy undergoing HSCT.

PROTOCOL TITLE: Randomized Trial of a Positive Psychology Intervention for Patients with Hematologic Malignancies Undergoing Hematopoietic Stem Cell Transplantation

Hypothesis: The PATH intervention will be deemed feasible with >75% of participants randomized to the intervention arm completing ≥ 6/9 positive psychology exercises. The PATH intervention will be deemed acceptable with mean ease and utility scores of each exercise being ≥ 7/10.

#2 (Effects on Patient-Reported Outcomes): To assess the preliminary efficacy of the PATH intervention on psychological (e.g., depression, anxiety, optimism, positive affect), QOL, and functional outcomes compared to the usual care condition.

Hypothesis: Patients randomized to the PATH intervention will have improved PPWB (e.g., optimism, positive affect, gratitude), mood (e.g., depression and anxiety), and QOL compared to those in the usual care condition.

#3 (Effects on Health Behaviors): To examine the impact of the PATH intervention on behavioral outcomes (e.g., medication adherence, physical activity) compared to those in the usual care condition.

Hypothesis: Patients randomized to the PATH intervention will have improved behavioral outcomes (e.g., medication adherence, physical activity) compared to those in the usual care condition.

2.0 Background*

Hematopoietic stem cell transplantation offers a potential cure for some hematologic malignancies.

Fifteen thousand allogeneic stem cell transplants are performed in the United States annually, and this number is projected to increase five-fold by 2030.²⁰ Notwithstanding the great promise for remission and survival, the experience of allogeneic transplantation is intense and prolonged, and it is accompanied by high rates of physical symptoms and a substantial risk of life-threatening complications and mortality due to chemotherapy-induced toxicities and early post-transplant complications.^{21,22-27} For example, 50-70% of patients undergoing HSCT experience moderate to severe nausea, diarrhea, pain, insomnia, and fatigue.^{24, 26} These symptoms, accompanied by the physical isolation during the prolonged HSCT hospitalization, often result in a rapid deterioration in psychological well-being and QOL throughout the early recovery post-HSCT.²⁶⁻²⁸

Psychological distress is common in hematopoietic stem cell transplant recipients.^{29,30,31} The prolonged hospitalization, social isolation, quarantine status, painful side effects, infections, and frequent outpatient follow-up visits can cause significant psychological distress even in the absence of formal psychiatric diagnoses.^{32,33,34} For example, 40% of patients report clinically significant depression and anxiety symptoms during HSCT.^{23, 24, 26} Further, several studies have consistently shown that symptoms of psychological distress (e.g., depression, anxiety) are prospectively associated with worse health outcomes, including decreased QOL, higher risk of graft vs. host disease (GVHD), and increased mortality.^{2, 35-37} Hence, patients with hematologic malignancies undergoing HSCT have significant physical and psychological needs, and interventions that reduce distress and its associated negative outcomes are needed for allogeneic transplant recipients.

Low levels of positive psychological well-being (PPWB) are also common in hematopoietic stem cell transplant recipients and have been independently associated with poorer health outcomes. Low levels of PPWB (e.g., optimism, positive affect) in allogeneic transplant recipients have also been associated with decreased QOL,³⁸ poorer immune response,³⁹ and increased mortality.⁴⁰ These poor health outcomes are likely mediated through deficits in health behaviors (e.g., medication adherence, physical activity),⁴¹ and indeed low PPWB has been prospectively associated with poorer adherence to diet, medication, and physical activity in other

PROTOCOL TITLE: Randomized Trial of a Positive Psychology Intervention for Patients with Hematologic Malignancies Undergoing Hematopoietic Stem Cell Transplantation

medical populations, independent of sociodemographic, medical comorbidity, and the ill effects of depression and anxiety.^{42, 43} In HSCT recipients, low PPWB and its associated effects on health behaviors are not only important in the short-term (e.g., for adherence to immunosuppressants), but also in the long term, as poor adherence to health behaviors can lead to secondary health problems (e.g., cardiovascular disease), low QOL, and increased mortality in cancer survivors.^{44,45} This suggests that enhancing PPWB in this population may have important behavioral and medical effects, and indeed such well-being in HSCT recipients is linked with improved QOL,⁴⁶ reduced fatigue and pain,⁴⁷ faster day to neutrophil engraftment,³⁹ and lower mortality.⁴⁰

Positive psychological interventions (PPIs) could be used to promote PPWB in the allogeneic transplant population. PPIs are interventions that encourage patients to systematically perform simple, enjoyable structured tasks and activities (e.g., writing a letter of gratitude, leveraging previous successes) that increase the intensity of positive thoughts and emotions.^{17, 48} A meta-analysis of 51 PPIs in >4000 participants found that PPIs enhance well-being and improve depressive symptoms, with effects persisting for up to 6 months.^{7, 49} Randomized trials of PPIs in medical populations (e.g., patients with coronary artery disease,¹¹ hypertension,¹⁰ or an acute coronary syndrome⁹) have found PPIs to be associated with greater PPWB, improved depression, improved QOL, greater medication adherence, and more physical activity.^{42, 50-53} PPIs are simple to administer and have been well-accepted by patients with a wide variety of illnesses.^{12, 54}

[figure not shown]
Scientific Premise of the Proposed Project: Despite the successful and effective use of PPIs in medical populations to reduce distress,^{9, 54} increase QOL, and promote health behaviors,⁵¹ they have never been tested in allogeneic recipients. Accordingly, informed by the Broaden and Build Theory of Positive Emotions,¹⁶ our team's efficacious PPI for cardiac patients,¹⁷ findings from prior work that explored PPWB in allogeneic recipients,¹⁸ we have developed the Positive psychology for Allogeneic Transplantation of Hematopoietic stem cell intervention (PATH), a novel 9-week phone-administered PPI. We have also completed a one-arm proof-of-concept study (18-225) to assess the feasibility and acceptability of the PATH intervention.¹⁹ We demonstrated that the PATH intervention was feasible and acceptable in patients undergoing HSCT and led to very small-to-medium effect size improvements in patient-reported outcomes such as optimism, positive affect, symptoms of depression and anxiety, QOL, and fatigue.¹⁹ This study established that a positive psychology intervention can be feasible in patients undergoing HSCT. Our findings from the proof-of-concept trial (18-225) suggest that the next step in this intervention development line of research is to conduct a randomized feasibility and preliminary efficacy trial to demonstrate feasibility and preliminary efficacy of the intervention in improving clinical outcomes. Findings from this single center randomized trial will lay the important groundwork for larger, multi-site randomized trials to establish efficacy.

Conceptual Model: Our conceptual model in Figure 2, adapted from the Broaden and Build Theory of Positive Emotions, proposes that PPWB increases patients' emotional and cognitive resources for problem-solving strategies and coping.¹⁶ Using this framework, we anticipate that our patient-centered, and low-burden PPI, the PATH intervention, will promote PPWB in patients with hematologic malignancies undergoing HSCT and could lead to improved HSCT outcomes (e.g., survival and GVHD severity)³ via decreased depression and anxiety,⁵⁵ and improved coping, QOL,^{42, 48} physical function,^{9, 56} and health behavior adherence.⁴⁸ (Figure 2)

PROTOCOL TITLE: **Randomized Trial of a Positive Psychology Intervention for Patients with Hematologic Malignancies Undergoing Hematopoietic Stem Cell Transplantation**

Figure 2. Conceptual Model

3.0 Inclusion and Exclusion Criteria*

We propose a single center randomized controlled trial of the PATH intervention versus usual care in 70 patients (age ≥ 18) with hematologic malignancies who have undergone HSCT. Participants will be recruited from the Dana Farber Cancer Institute (DFCI) HSCT Program. Participants will be randomized equally to the two arms using randomized permuted blocks of sizes two and four, with randomization stratified by presence/absence of graft versus host disease (GVHD). As allogeneic transplant recipients with GVHD have significantly different courses of recovery, QOL, and function post-transplant, we will stratify by GVHD status to ensure adequate and balanced representation between the two study groups.

3.1 Screening Procedures:

Eligible study participants will be identified using the DFCI HSCT clinic database. The clinical research coordinator (CRC) will review the database to screen for eligible patients. We have utilized this study procedure in our proof-of-concept trial (18-225) and enrolled 56% of potentially eligible participants.

Patients who have been approved for the study by their HSCT oncologist will be contacted twice via telephone or in person at a routine clinic visit by a member of the study team after inclusion/exclusion criteria is assessed. Eligible patients will be screened and provided (in-person at clinic, mailed or e-mailed) an information sheet (Appendix A) of the study to review prior to their completing consent procedures.

PROTOCOL TITLE: Randomized Trial of a Positive Psychology Intervention for Patients with Hematologic Malignancies Undergoing Hematopoietic Stem Cell Transplantation

The DFCI will register eligible participants in the Clinical Trials Management System (CTMS) OnCore as required by DF/HCC SOP REGIST-101. When required by REGIST-101, registration must occur prior to the initiation of protocol-specific procedures or assessments.

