4.0 Study-Wide Number of Subjects*

We propose to recruit 70 patients with hematologic malignancies who have undergone HSCT from one site – DFCI. This is not a multi-site study.

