Participants will be registered with the Clinical Trials Management System after they have consented, provided baseline *Actigraph GT3X+* data, and completed baseline assessments. If participants provide consent but do not complete baseline Actigraph data collection and assessments, they will not count towards accrual numbers. Participants who withdraw from the study or die during the study period will not be replaced and they will count towards accrual numbers.

DF/HCC institutions will register eligible participants in the Clinical Trials Management System (CTMS) Oncore as required by DF/HCC SOP REGIST-101. Registration must occur after the initiation of protocol-specific procedures or assessments.

For registration of participants from the DF/HCC institutions, study staff will complete the DF/HCC protocol-specific eligibility checklist. Study staff will confirm that the participant meets all inclusion criteria as described in this protocol. Study staff will then register study participants through OnCore. Study staff will follow DF/HCC Standard Operating Procedure for Human Subject Research Titled *Subject Protocol Registration* (SOP #: REGIST-101) and register the participant on the protocol.

Once the patient has been registered, a member from the MGH Cardiac Psychiatry Research Program (CPRP) team or the Cancer Outcomes Research and Education Program (CoRE) (independent from the study staff) will perform randomization procedures using a computer-generated randomization schema, stratified by GVHD status.

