6.0 Multi-Site Research

Not Applicable. This research is located at one site – the DFCI main campus

7.0 Study Timelines*: Table 1 depicts the expected study timeline.

Time Point	Table 1: Study Procedure
Months 0-2	Finalize protocol development and submit to Institutional Review Board for approval
Months 3-4	Staff Training ❖ Hire CRC and train them in study procedures, recruitment, and data collection.
Months 5-29	Randomized Controlled Trial: ❖ Enroll and randomly assign 70 patients (35 per study group) to receive either the PATH intervention vs. usual care control.
Months 30-35	Data Collection: ❖ Complete longitudinal data collection with a minimum of 1 year follow-up on all study participants.
Months 36-40	Data Analysis: ❖ Complete data analysis and submit primary manuscripts. ❖ Prepare and submit grant proposal for large scale multi-site randomized controlled efficacy study.

PROTOCOL TITLE: Randomized Trial of a Positive Psychology Intervention for Patients with Hematologic Malignancies Undergoing Hematopoietic Stem Cell Transplantation

Each participant will be enrolled for approximately one year to collect patient-reported outcomes. We estimate that we will complete the primary manuscripts in months 57-60 from the study start period.

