9.0 Procedures Involved*

9.1 Study Design

We propose a single center randomized trial of a positive psychology intervention (PATH) versus usual care in 70 patients with hematologic malignancies undergoing HSCT. Participants will be randomized equally to the two arms using randomized permuted blocks of sizes two and four, with randomization stratified by presence/absence of GVHD. As allogeneic transplant recipients with GVHD have significantly different courses of recovery, QOL, and function post-transplant, we will stratify by GVHD status to ensure adequate and balanced representation between the two study groups.

PROTOCOL TITLE: Randomized Trial of a Positive Psychology Intervention for Patients with Hematologic Malignancies Undergoing Hematopoietic Stem Cell Transplantation

The goals of this study are to assess the feasibility, acceptability and preliminary efficacy of this novel 9-session, weekly PP-based intervention for HSCT patients.

Patients will be contacted via telephone or in person at a routine clinic visit close to their routine 70-80-day post-transplant visit for eligibility determination. Interested patients will be screened based on the inclusion/exclusion criteria and provided a study information sheet via mail, e-mail or in-person at a routine clinic visit. Consent procedures would be completed in-person at a routine clinic visit or verbally over the phone approximately seven days after study information is provided.

Upon consent to participate in the study, participants will be given an electronic pill bottle (MEMS Cap) [to be used from the time of baseline assessment completion through the entire duration of the intervention], and an accelerometer to be worn for 7 days prior to the initiation of the intervention. Between the 85-95-day point, all participants will also complete baseline questionnaires either in person, over phone or via a REDCap survey link to participants. Additionally, participants randomized to the intervention group will be given an intervention manual with 9 weekly PP exercises.

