9.7 Overview of Research Procedures

Initial/Enrollment phone call: During this initial approach at a routine outpatient follow-up clinic or phone call, the study procedures will be explained to potential participants. Those who are interested will be screened for eligibility and, mailed or e-mailed a copy of the study information

PROTOCOL TITLE: Randomized Trial of a Positive Psychology Intervention for Patients with Hematologic Malignancies Undergoing Hematopoietic Stem Cell Transplantation

sheet. We will then call patients upon receipt of the information sheet approximately seven days from receipt of the information sheet for enrollment and written consent procedures during a routine clinic visit or verbal consent procedures over the phone. Consented participants will then be randomized to usual care or the intervention group. All participants will be mailed (or given in person at a routine follow-up visit) the electronic pill bottle (MEMS Caps), and the accelerometer (Actigraph GT3X+, small half-dollar sized device that clip on to a belt with no visible readout thus preventing independent subject access to data) to wear for 7 days prior to the intervention initiation in the control group. Participants in the intervention group will also be mailed the study intervention manual together with their accelerometer and electronic pill bottle. At the time of the baseline survey and prior to the start of the intervention, adequate accelerometer wear (at least 4 days with 10+ hours per day worn) will be confirmed. Participants in the intervention group will also be mailed the study intervention manual. Those who have not completed sufficient wear of the device will be asked to re-wear the device until there is sufficient baseline data available.

Baseline Assessments: Around the time of each participant's routine 85-95-day post-transplant routine clinic visit, participants will be asked to complete baseline assessment questionnaires either in person during a routine follow-up visit in clinic, over phone, or via a REDCap survey link that will be e-mailed to participants.

After completion of the baseline survey and a returned accelerometer with adequate data, the interventionist will review the mailed treatment manual with weekly PP exercises to those in the intervention group. Participants in the intervention group will be assigned the first exercise (gratitude for positive events) in preparation for their first phone session.

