19.0 Resources Available

19.1 Team Qualification and oversight

The PI of the project ([name]) is responsible for full oversight of the project. She will be meeting with the research coordinator on weekly basis (and more often as urgent issues arise) to ensure the study process is being followed accurately and to address potential challenges or issues as they may arise. [name] is a member of the MGH Cancer Outcomes Research Program (CORe). CORe has extensive experience conducting randomized clinical trials of supportive care interventions in oncology and has the necessary expertise to ensure the success of the proposed project. [name] is also a member of the MGH Cardiac Psychiatry Research Program (CPRP) which has extensive expertise in conducting positive psychology based intervention studies in patients with serious illnesses – resources from the CPRP will help to ensure the success of the project.

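### The protocol prints permuted block sizes of two and four for a single-centre trial whose recruiting staff can see past allocations, so about 72% of next assignments could be guessed and about 11% known at the moment of registration

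*Combined protocol and SAP*

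**What the plan says.** - **Allocation method.** Section 3.0 specifies "randomized permuted blocks of sizes two and four, with randomization stratified by presence/absence of graft versus host disease (GVHD". Section 9.1 repeats the sizes: "randomized permuted blocks of sizes two and four, with randomization stratified by presence/absence of GVHD". The ratio is 1:1; section 3.0 puts it as "Participants will be randomized equally to the two arms".
- **Size and setting.** Table 1 in section 7.0: "Enroll and randomly assign 70 patients (35 per study group". Section 4.0: "This is not a multi-site study".
- **Who allocates, and when.** Section 5.1 puts randomisation after baseline and registration. The person doing it is "independent from the study staff) will perform randomization procedures using a computer-generated randomization schema, stratified by GVHD status". Section 21.0 also places it after registration. Section 9.7 instead has participants randomised once they have consented, before it describes device wear and the baseline survey.
- **Who recruits.** Under section 5.1 the coordinator screens the database, asks the treating clinician about concerns and approaches the patient. Section 11.0 trains the same role to obtain consent and to follow participants over time.
- **Who can see the arm.** Section 9.7: "Participants in the intervention group will also be mailed the study intervention manual together with their accelerometer and electronic pill bottle". Weekly calls and the exit interview also go to one arm only (section 9.1). The research team reviews retention and dropout by treatment group every week (section 11.0). The only blinded role mentioned is the coordinator who double-enters 10% of the data (section 10.4).

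The documents do not say how often each block size is used, or that the sizes are withheld from anyone.

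**The concern.** Concealing the list protects against someone reading the next assignment. It does not protect against someone working it out. In blocks of two and four the running imbalance within a stratum never exceeds 2. At an imbalance of 2 the next arm is fixed, and at an imbalance of 1 the lagging arm is favoured. A team that sees every past allocation in two short sequences, and has the sizes in its own protocol, has all it needs to predict.

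At stake is the order in which patients who are ready at about the same time are registered. The primary feasibility measure is taken only in PATH, against a threshold of more than 75%. One patient in 35 is 2.9 percentage points: 26/35 = 74.3% fails and 27/35 = 77.1% passes. In Aim 3, section 10.1 first compares steps per day at weeks 9 and 18 by a Wilcoxon rank sum test with no baseline adjustment, so a difference in who was registered to which arm passes straight into that test.

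**Working it through.** The plan states no figure for predictability, so there is none to reproduce.

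**Inputs.** From the documents: block sizes 2 and 4, 1:1 allocation, two GVHD strata, 70 patients. Assumed: each size equally likely (varied below), and an observer who knows the possible sizes and the past sequence in each stratum, but not the size of the current block.

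**Share guessed, long run.** The rule is to guess the arm that is behind and toss a coin at a tie.
- Block of 2: 1/2 + 1 = 3/2 correct.
- Block of 4: the patterns AABB, ABAB and ABBA (and their mirror images) give 2.5, 3 and 3 correct, a mean of 17/6.
- With p the probability of size 2, share guessed = [p × 3/2 + (1 − p) × 17/6] / [2p + 4(1 − p)].
- At p = 1/2: (0.750 + 1.417) / 3 = 13/18 = 72.2%.

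**Share known with certainty.** An imbalance of 2 arises only in a block of 4 that opens AA or BB (probability 1/3), and it fixes the next two assignments.
- Share certain = (1 − p) × (1/3) × 2 / [2p + 4(1 − p)].
- At p = 1/2: 0.333 / 3 = 1/9 = 11.1%.

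**Sensitivity to the unstated mix, and to 70 patients.** The last two columns are simulations of the best possible guesser, with strata of 10/60, 20/50 and 35/35.

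| P(size 2) | Guessed, long run | Certain, long run | Guessed, 70 patients | Certain, 70 patients |
|---|---|---|---|---|
| 1/3 | 71.7% | 13.3% | 70.9–71.4% | 12.8% |
| 1/2 | 72.2% | 11.1% | 71.6–72.0% | 10.8% |
| 2/3 | 72.9% | 8.3% | 72.2–72.8% | 7.9–8.0% |

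**Looking further ahead, and the alternative.** Best guesser, strata of 35, sizes equally likely and known:

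| Blocks | Next slot: guessed (certain) | One slot further | Two slots further |
|---|---|---|---|
| 2, 4 | 71.5% (10.6%) | 55.5% | 52.8% |
| 4, 6, 8 | 67.3% (2.4%) | 59.7% | 56.5% |

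**Which slot the earlier decisions concern.** Patients are approached around day 70–80 and baseline is around day 85–95, so about 15 days separate the two. Section 19.2 plans 5–6 enrolments a month, giving about 2.5–3 registrations in half a month. Table 1 allows 25 months: 70/25 = 2.8 a month, or about 1.4 in half a month. If the strata are equal in size (assumed), about 0.7 to 1.5 of these fall in the patient's own stratum. A judgement made at approach therefore typically concerns a slot about one further on, sometimes two, where the guess is much weaker.

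**The case against.** **Safeguards exist.** Block sizes vary, the schema is computer-generated, and someone independent of the study staff allocates after registration. This stands as protection of the list. It does not stop prediction from past assignments.

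**The discretion mostly comes too early and belongs to others.** Concerns about a patient, and the exclusion for conditions thought to prevent compliance, are the treating clinician's, with the reason for a concern documented. Nothing suggests that clinicians track allocations. The accelerometer re-wear rule is a fixed criterion, and the day 85–95 baseline and day-100 start limit delay. This largely stands. What remains is the order of registrations that fall close together.

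**Larger blocks are not better at every horizon.** One or two slots further on, blocks of 4, 6 and 8 are somewhat more guessable than 2 and 4 if their sizes are known. This stands, and it is why withholding the sizes matters as much as enlarging them.

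**Stronger readings that the documents do not support.**
- A reader might infer a materially raised type I error for Aim 2, or a much better chance of passing the feasibility threshold. Either needs an assumed strength of steering, for which the documents give no basis. For Aim 2, section 10.1 models the difference in change from baseline, so a stable difference already present at baseline largely cancels and only selection on future course survives. Its stated level is 0.2 with a Bonferroni correction, and section 10.2 says the pilot is not designed to detect group differences definitively.
- A reader might doubt the list holder's independence because section 19.1 says a team member "is also a member of the MGH Cardiac Psychiatry Research Program (CPRP", one of the programmes that supplies the randomiser. Names are removed there, and shared membership does not show access to the list.
- A reader might take 72% as a forecast. It is a ceiling for someone who tracks every allocation in order and by stratum.

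**Conclusion.** The point holds as a weakness in allocation concealment that is cheap to avoid. At the moment of registration about 72% of next assignments could be guessed (71–73%) and about 11% known (8–13%), against 50% and 0% under simple randomisation. The first figure barely depends on the unstated mix of block sizes; the second depends on it more.

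The conclusion rests on two readings. First, recruiting staff can see past allocations: the documents never call the trial open, but the procedures differ visibly by arm and no masking of recruiters is described. Second, the sizes are available to those staff, since they are printed in the protocol and nothing restricts them.

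Exposure is greatest for the PATH-only feasibility rate and the unadjusted Aim 3 Wilcoxon test, and smaller for Aim 2. No size of bias can be derived from the documents, and none is claimed.

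The conflict between sections 5.1 and 9.7 makes it worse. If patients are randomised at consent, the arm can be known before baseline is complete, yet section 5.1 does not count patients without baseline data towards accrual.

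**What to change.** 1. In sections 3.0 and 9.1, delete the stated block sizes. Say only that allocation uses randomly varied permuted blocks, stratified by GVHD status.
2. Generate the list for patients not yet randomised with larger varied blocks, for example 4, 6 and 8. At the next slot this gives about 67% guessed and 2% certain even if the sizes became known.
3. Keep the sizes in a restricted document not available to recruiting staff, the principal investigator or the interventionists.
4. Reconcile section 9.7 with sections 5.1 and 21.0, so that each assignment is released only after baseline is complete and registration is locked with GVHD status recorded. Move the mailing of the manual accordingly. Sections 5.1 and 21.0 also disagree on whether registration comes after or before protocol-specific procedures begin, and this should be settled in the same edit.

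**Cost.** A short amendment and a new list; no extra patients, visits or staff. The largest possible imbalance per stratum rises from 2 to 4. In the worst case over both strata the split is 39/31 instead of 37/33. Relative to 35/35, the variance of a difference in means is proportional to 1/39 + 1/31 = 0.0579 against 2/35 = 0.0571, an increase of about 1.3%. If the new sizes leaked, predictability one and two slots further on would be about 60% and 56–57%, against about 56% and 53% now.
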